4.2. Experimental design

4.2.1. Study plan

This is a randomized, multicenter, double-blind, placebo-controlled, parallel-group doseranging study which will be conducted in study centers in Russian Federation.

The study will consist of 3 periods: selection period up to 2 weeks, double-blind treatment period for 12 weeks + Follow up period for 2 weeks after double-blind treatment stop. The study plan is shown in Figure 1.

Figure 1. Study plan

Study periods Selection Period Double-blind Follow-Up treatment period (luseogliflozin or placebo) ASSE W-2W4**W8** W14 $\mathbf{W0}$ W12 $(\pm 3 \text{ days})$ (-14 days max) $(\pm 3 \text{ days})$ $(\pm 3 \text{ days})$ $(\pm 3 \text{ days})$ $\mathbf{D0}$ Selection Inclusion End of IMP **EoS** Randomization

Ongoing treatment with metformin

	No IMP	Luse	ogliflozin 2,5 mg gro	up (n=80)		No IMP
	No IMP	Luse	eogliflozin 5 mg grou	p (n=80)		No IMP
	No IMP	Luse	eogliflozin 10 mg grou	up (n=80)		No IMP
	No IMP		Placebo group (n=80)			No IMP
ASSE		W0	W4	W8	W12	W14

Selection period will precede the inclusion into the study once the informed consent is signed and will last 7- 14 days before the randomization into the study to confirm the eligibility of the patients. Treatment with metformin in stable (during the previous 3 months) dose should be continued, the dosage frequency of metformin should be also unchanged. Diet and physical activity as routinely advised to the diabetic patients should be followed.

At inclusion visit the eligible patients will be randomized to receive either 2.5 mg, 5 mg, 10 mg Luseogliflozin or placebo in 1:1:1:1 manner. Randomization will be stratified on HbA1c (< 8.5% and $\ge 8.5\%$) and center (stratum 'center performing PK sampling' and another one 'center not performing PK sampling').

The patients will start Luseogliflozin and/or placebo next day after inclusion visit in addition to the ongoing treatment with metformin.

After randomization the patients will undergo 4 study visits: Week 4 (W4), Week 8 (W8), Week 12 (W12) visits and the End of Study (EoS) follow up visit in 2 weeks after double-blind treatment stop (W14).

During the double-blind treatment the doses of luseogliflozin and metformin as well as dosage frequency of metformin should not be changed unless for safety reasons (e.g. hypoglycaemia); antidiabetic medications other than metformin are not allowed during the selection period and double-blind treatment period, except in case of rescue therapy (see section 6.3.1).

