5.7. Participant withdrawal

5.7.1. Withdrawal criteria

- $HbA1c \ge 11.0\%$
- Fasting plasma glucose ≥ 270 mg/dl (15.0 mmol/l) at two consecutive visits or if identified by SMBG and confirmed with lab testing before withdrawal or rescue therapy

- Major hypoglycaemia defined as symptoms requiring the assistance of another person due to disturbance of consciousness associated with hypoglycemia
- Sustained decrease of eGFR to 30 ml/min/1.73 m2 or ≥ 50% compared to the baseline

Furthermore, participation in the clinical study could be discontinued by the investigator or by the sponsor for any of the following reasons:

- Adverse events according to the judgement of the investigator (presents a risk to the participant or requires prescription of a treatment which is incompatible with the protocol or significant alteration of laboratory parameters). Continuation of a subject in the PK sampling who experiences emesis or diarrhea following drug administration will be evaluated on a case by case basis;
- **Major deviation to protocol** if it interferes with the study evaluations and/or if it jeopardises participant's safety
- The subject is uncooperative during the study
- **Non-medical reason**, e.g. consent withdrawal.

A complete final evaluation should be made at the time of the subject's withdrawal, and an attempt should be made to perform a follow-up evaluation. Information to be collected should be as at Week 12 visit as indicated in Table 1. The follow-up visit should be planned after 2 weeks from the IMP stop to perform investigations as for W14 visit.

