6.3. Previous and concomitant treatments

Information on previous treatment taken by the patient within 3 months prior to selection and stopped by the time of selection (previous treatment) as well as administered during the study (regarded as concomitant treatment) must be documented in the patient's medical records and on the appropriate eCRF pages. Any changes to the concomitant medications during the study need to be clearly recorded and the reason for the change should be documented.

Use of the following medications is prohibited during the study unless the patient requires rescue medication due to loss of glucose control as taking these drugs will affect the study endpoints:

- Insulin (within 3 months prior to selection and until the end of double-blind treatment (visit Week 12))
- Thiazolidinediones (within 3 months prior to selection and until the end of double-blind treatment (visit Week 12))

- Sulphonylureas, nateglinide, DPP4 inhibitors, alpha-glucosidase inhibitors, or GLP-1 analogues (within 3 months prior to selection and until the end of double-blind treatment (visit Week 12))
- SGLT2 inhibitors (within 1 year prior to selection and until Week 14)
- Anti-obesity drugs
- Oral or parenteral corticosteroids

Use of the following medications will be allowed during the study, provided that the subject has been on a stable dose for at least 6 weeks prior to selection:

- Beta-blockers
- Thyroid-hormones
- Antihypertensive drugs
- Diuretics
- Drugs for treatment of dyslipidaemia

The changes in concomitant treatment during the study will not systematically constitute a reason to withdraw a patient from the study, other that if the patient's safety is compromised or if it interferes with the study evaluation. The sponsor must be contacted before deciding to withdraw a patient in such context.

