6.3.1. Rescue treatment for loss of glucose control

The patients with loss of glucose control according to the following criteria will be prescribed rescue treatment during the double blind period of the study and will be allowed to remain in the study:

- Week 1-4: glucose level at SMBG or at the visit 240-270 mg/dl (13.3-15.0 mmol/l) inclusive after overnight fast or >400 mg/dl (>22.2 mmol/l) in a randomly performed measurement
- Week 4-12: glucose level at SMBG or at the visit 220-270 mg/dl (12.2-15.0 mmol/l) inclusive after overnight fast or >400 mg/dl (>22.2 mmol/l) in a randomly performed measurement

Insulin therapy may be instituted as needed. Alternatively, at the discretion of the Investigator, other antidiabetic medication can be prescribed; SGLT 2 inhibitors are not allowed as rescue therapy.

A complete final evaluation should be made before initiation of rescue therapy, if possible. Information to be collected should be as at Week 12 visit as indicated in Table 1 5.7.2

The details of rescue medications should be recorded in the e-CRF.

In case of hypoglycaemia that may put the patient on risk (e.g. repeated symptomatic hypoglycaemia or major hypoglycaemia), appropriate dose adjustment of antidiabetic therapy such as dose reduction/discontinuation of ongoing rescue medication or existing background therapy should be imitated. Reduction or discontinuation of ongoing rescue medication should be considered before a reduction in the dose of existing background therapy.

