8.2.4. Blood glucose monitoring

Fasting blood glucose will be measured at selection, inclusion, Week 4, Week 8 and Week 12 in a local laboratory. In addition, during the study the patients will perform SMBG at home using a glucose meter and the test strips provided for the study:

- Selection period: One measurement every day in a fasting state before breakfast.
- After inclusion (during double-blind treatment period and until Week 14): One measurement every day in a fasting state before breakfast and 4 measurements during a day (including preprandial and postprandial state) once a week

SMBG can be performed more frequently, if necessary, according to investigator's judgement. The patient will record information in the study diary provided by the investigator at the visits. Patients experiencing symptoms of hypoglycaemia will also perform a blood glucose self-measurement at the time of the event.

The patients should be instructed to contact the investigator:

- If they record blood glucose levels equal or less than 3.9 mmol/L (70 mg/dL) at any time during the study. The investigator will determine whether the patient should return to the site for further assessment. In addition, the patient should be instructed on recognition of the symptoms of hypoglycaemia and requested to measure glucose by glucose meter when they experience these symptoms.
- If, between Inclusion and Week 4 the fasting glucose is equal or above 240 mg/d (13.3 mmol/l), and between Week 4 and Week 12 is equal or above 220 mg/gl (12.2

mmol/l) the investigator should make every effort to have the patient visit to the clinic for a fasting plasma glucose measurement as soon as possible but within 7 days as maximum.

Glucometer readings should be printed out at each study visit and kept in the patient's medical file.

The measurements of SMBG will not be recorded in the e-CRF, except in case of AE reporting.

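### Rescue stops at 270 mg/dl and withdrawal above it needs confirmation, so a lone visit fasting glucose of 271–400 mg/dl has no mandated action

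*Protocol*

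**What the plan says.** Rescue is defined in Protocol section 6.3.1 by two time bands. The first is "Week 1-4: glucose level at SMBG or at the visit 240-270 mg/dl (13.3-15.0 mmol/l) inclusive after overnight fast" and the second is "Week 4-12: glucose level at SMBG or at the visit 220-270 mg/dl (12.2-15.0 mmol/l) inclusive after overnight fast". In either period a random value above 400 mg/dl also qualifies. Patients who meet these criteria "will be prescribed rescue treatment during the double blind period of the study and will be allowed to remain in the study". No confirmation step is given there.

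Withdrawal is defined in section 5.7.1. For fasting plasma glucose the threshold is 270 mg/dl or more, and it counts "at two consecutive visits or if identified by SMBG and confirmed with lab testing before withdrawal or rescue therapy". The same section lets the investigator discontinue a patient for an adverse event, which includes a significant change in laboratory values. No glucose level is attached to that route.

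Two other sections bear on whether a site may give rescue outside the 6.3.1 bands. Section 6.3 lists antidiabetic drugs as "prohibited during the study unless the patient requires rescue medication due to loss of glucose control", which is general. Section 4.2.1 bars other antidiabetic drugs through the "double-blind treatment period, except in case of rescue therapy (see section 6.3.1"), which sends the site back to the bands.

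Monitoring is in section 8.2.4. For the laboratory: "Fasting blood glucose will be measured at selection, inclusion, Week 4, Week 8 and Week 12 in a local laboratory". At home after inclusion: "One measurement every day in a fasting state before breakfast and 4 measurements during a day", the latter once a week. A home fasting value of 240 mg/dl or more up to Week 4, or of 220 or more afterwards, calls for a clinic fasting measurement within 7 days at most. That recall has no upper limit.

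**The concern.** Rescue and withdrawal should form one ladder, in which a higher fasting glucose never brings a weaker instruction. Here the rescue band has a closed top at 270 mg/dl, and the next rung needs a second piece of evidence. A single visit value just above the top therefore falls between the two rules, although a lower value on the same day makes rescue mandatory.

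Three boundary faults come with it:

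- 270 belongs to both rules once it is confirmed, and their outcomes are opposite: stay in the study on rescue, or leave it.
- The W4 visit belongs to both rescue bands, which have different floors.
- The confirmation of home readings that 5.7.1 names before rescue is absent from the section that governs rescue.

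At stake is whether a patient with poor control is acted on, and whether sites act alike on the same reading. Rescue and withdrawal also decide which HbA1c values are imputed under section 10.1, so the question of an effect on the primary analysis has to be asked.

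**Working it through.** **Inputs.** Rescue bands and the random rule: 6.3.1. Withdrawal threshold and confirmation: 5.7.1. Visits at W4, W8 and W12, each ±3 days: 4.2.1 and Table 1. Home testing and recall: 8.2.4. Imputation: 10.1.

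**Unit check.** With 18.016 mg/dl per mmol/l: 220/18.016 = 12.2, 240/18.016 = 13.3, 270/18.016 = 15.0, 400/18.016 = 22.2. These match the protocol, so the faults are not conversion errors.

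**Rule map.** The two sections were applied literally to fasting values in whole mg/dl. Confirmed means two consecutive visits, or a home value confirmed by the laboratory.

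| Fasting value and evidence | 6.3.1 | 5.7.1 | Outcome |
|---|---|---|---|
| 230, W8, single visit | rescue | not met | rescue |
| 270, W8, single visit | rescue | not met | rescue |
| 270, W8, confirmed | rescue | withdraw | two rules apply |
| 271, 300 or 399, week 2, 4 or 8, single visit | not met | not met | nothing mandated |
| 271, 300 or 399, confirmed | not met | withdraw | withdraw |
| 220–239, W4, single visit | met for Week 4–12, not for Week 1–4 | not met | depends on the band chosen |
| 240–269, W4, single visit | met for both bands | not met | rescue |

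**Width of each fault.** The firm gap is 271–400 mg/dl. Above 400 the random-measurement rule might be read to apply. The 270 overlap is one value. The W4 overlap is 239 − 220 + 1 = 20 whole values.

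**Time to the next scheduled visit.** W4 is day 28 ± 3 (25–31), W8 is day 56 ± 3 (53–59) and W12 is day 84 ± 3 (81–87). From one visit to the next, the minimum is 53 − 31 = 22 days, the nominal interval 28, and the maximum 59 − 25 = 34. If only scheduled post-randomisation visits count, W4 + W8 is the only pair that can end treatment early, because W8 + W12 completes at the end of treatment.

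**Confirmation.** Section 5.7.1 names laboratory testing before rescue as well as before withdrawal. Section 8.2.4 orders the clinic measurement. Section 6.3.1 accepts a value at home or at the visit and says nothing about confirming it.

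**Primary analysis.** Section 10.1 multiply imputes both missing W12 HbA1c and HbA1c collected after rescue. In the primary analysis, a rescued patient and a withdrawn patient without a W12 value are therefore both imputed. A patient with 280 and no action would contribute an observed value. The protocol gives no rescue or withdrawal rate, so the number of such patients cannot be calculated.

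**The case against.** The strongest answer is that the gap is mostly closed by other parts of the protocol. Visits take place in the morning while fasting (7.2), fasting home testing is daily, and the meter is reviewed at every visit after selection (Table 1). A patient whose visit sample is above 270 will usually have a meter reading from that morning. If it is also 270 or more, the visit sample can itself serve as the laboratory confirmation, and withdrawal applies at once. On later days, a home value from 220 to 270 triggers rescue, and any value at or above the floor triggers the recall. Discretionary withdrawal is available, and HbA1c of 11.0% or more, measured at W8 and W12, is a separate withdrawal criterion. What remains is mainly the case in which meter and laboratory disagree. This stands, and it is why the point is minor. It does not remove the inversion in the mandated actions.

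The smaller points also have fair answers. Neither rescue band forbids rescue, so a W4 value of 220–239 can be treated under the later band. Rescue at a first 270 followed by withdrawal on confirmation can be read as a sequence. Sections 5.7.1, 6.3.1 and 8.2.4 read together give home value, recall, laboratory, action. That makes the confirmation issue an omission in 6.3.1 rather than a proven contradiction. Each reading is reasonable, but a site has to supply it.

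A reader might infer that such patients are routinely left untreated for 22 to 34 days. That is a worst case: for the whole interval, no home fasting value may trigger rescue or lead to a confirmed 270 or more, or the recall must fail. A reader might also infer that the primary result is biased. The document supports neither a size nor a direction.

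**Conclusion.** The point holds as a minor safety and consistency defect. For a single visit fasting value of 271–400 mg/dl without a matching home reading, the protocol mandates nothing and leaves discretionary withdrawal. It mandates rescue at 240–270 up to Week 4 and at 220–270 afterwards. A confirmed 270 and a W4 value of 220–239 each fall under two rules, and 6.3.1 is silent on a confirmation that 5.7.1 names.

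This rests on a literal reading of both sections, on treating the general mention of rescue in 6.3 as permission rather than a requirement, and on whole mg/dl values. The number of patients affected is unknown and probably small, given the monitoring in 8.2.4. No effect on the primary analysis is demonstrable.

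**What to change.** Amend 6.3.1 and 5.7.1 as follows.

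(a) Remove the 270 upper limit and assign W4 to one band: before the W4 visit, fasting 240 mg/dl or more; from the W4 visit to W12, fasting 220 or more. Any single visit laboratory value at or above the floor then triggers rescue, unless the 5.7.1 withdrawal criterion is already met.

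(b) State that a confirmed fasting glucose of 270 or more leads to withdrawal and takes precedence over rescue. Confirmation is a second visit or recall value, or a home value confirmed by the laboratory, including by that visit's own sample.

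(c) State in 6.3.1 that home readings are confirmed through the 8.2.4 recall, within 7 days, before rescue.

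Under these rules a lone visit value of 280 at W8 is rescued, as 230 is. A confirmed 270 is withdrawn, and 230 at W4 is rescued. Requiring a repeat test before acting on a single visit value of 270 or more would be a poorer choice: 230 would be treated at once, while 300 waited and might get no action.

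The cost is amendment text and site retraining. Rescue on a home reading alone would wait for the clinic measurement that 8.2.4 already asks for.

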5.7.2. Procedure

In the case of premature withdrawal from the study due to an adverse event (event requiring immediate notification or not), the investigator must make every effort to collect the information relating to the outcome of the event. If necessary, the information will be collected afterwards (see section 8.9.2.2). This information is recorded in that part of the e-CRF which concerns adverse events. If the investigator cannot collect the information from a visit, he must collect it from the doctor ensuring the follow-up of the participant.

If the study is stopped / IMP is discontinued as a result of an event requiring immediate notification, the procedure described in section 8.9.2.4 is to be implemented.

The dispositions to be taken after the IMP discontinuation are described in section 6.5.

5.7.3. Lost to follow-up

When the investigator has no news of the participant, he/she must make every effort to contact him/her or a person around him/her (phone calls, letters including registered ones...etc.), to establish the reason for the discontinuation of IMP and to suggest the participant comes to an end-of-study visit. If all these attempts to contact the participant fail, the investigator can then declare the participant "lost to follow-up". The investigator should document all these attempts in the corresponding medical file.

6. TREATMENT OF PARTICIPANTS

6.1. IMPs administered

Investigational medicinal product (IMP): Luseogliflozin and matching placebo in tablets for oral administration once daily (before breakfast)

Dose regime:

Patients will have to take 3 tablets of IMP per day (in addition to the ongoing treatment with metformin) as follows:

- 2.5 mg group: one tablet of Luseogliflozin 2.5 mg, one tablet of Placebo 2.5 mg and one tablet of Placebo 5 mg
- 5 mg group: two tablets of Luseogliflozin 2.5 mg and one tablet of Placebo 5 mg
- 10 mg group: two tablets of Luseogliflozin 2.5 mg and one tablet of Luseogliflozin 5 mg
- Placebo group: two tablets of Placebo 2.5 mg and one tablet of Placebo 5 mg

6.2. IMPs dispensing

Investigator will use IRS to perform the following:

- To create the patient's number (at ASSE)
- To randomize the patient and allocate the treatment at W0 visit
- To allocate the treatment at W4 and W8 visits

The IMP will be dispensed on the inclusion (randomization) visit and at the study visits at Week 4 and Week 8.

6.3. Previous and concomitant treatments

Information on previous treatment taken by the patient within 3 months prior to selection and stopped by the time of selection (previous treatment) as well as administered during the study (regarded as concomitant treatment) must be documented in the patient's medical records and on the appropriate eCRF pages. Any changes to the concomitant medications during the study need to be clearly recorded and the reason for the change should be documented.

Use of the following medications is prohibited during the study unless the patient requires rescue medication due to loss of glucose control as taking these drugs will affect the study endpoints:

- Insulin (within 3 months prior to selection and until the end of double-blind treatment (visit Week 12))
- Thiazolidinediones (within 3 months prior to selection and until the end of double-blind treatment (visit Week 12))

- Sulphonylureas, nateglinide, DPP4 inhibitors, alpha-glucosidase inhibitors, or GLP-1 analogues (within 3 months prior to selection and until the end of double-blind treatment (visit Week 12))
- SGLT2 inhibitors (within 1 year prior to selection and until Week 14)
- Anti-obesity drugs
- Oral or parenteral corticosteroids

Use of the following medications will be allowed during the study, provided that the subject has been on a stable dose for at least 6 weeks prior to selection:

- Beta-blockers
- Thyroid-hormones
- Antihypertensive drugs
- Diuretics
- Drugs for treatment of dyslipidaemia

The changes in concomitant treatment during the study will not systematically constitute a reason to withdraw a patient from the study, other that if the patient's safety is compromised or if it interferes with the study evaluation. The sponsor must be contacted before deciding to withdraw a patient in such context.

6.3.1. Rescue treatment for loss of glucose control

The patients with loss of glucose control according to the following criteria will be prescribed rescue treatment during the double blind period of the study and will be allowed to remain in the study:

- Week 1-4: glucose level at SMBG or at the visit 240-270 mg/dl (13.3-15.0 mmol/l) inclusive after overnight fast or >400 mg/dl (>22.2 mmol/l) in a randomly performed measurement
- Week 4-12: glucose level at SMBG or at the visit 220-270 mg/dl (12.2-15.0 mmol/l) inclusive after overnight fast or >400 mg/dl (>22.2 mmol/l) in a randomly performed measurement

Insulin therapy may be instituted as needed. Alternatively, at the discretion of the Investigator, other antidiabetic medication can be prescribed; SGLT 2 inhibitors are not allowed as rescue therapy.

A complete final evaluation should be made before initiation of rescue therapy, if possible. Information to be collected should be as at Week 12 visit as indicated in Table 1 5.7.2

The details of rescue medications should be recorded in the e-CRF.

In case of hypoglycaemia that may put the patient on risk (e.g. repeated symptomatic hypoglycaemia or major hypoglycaemia), appropriate dose adjustment of antidiabetic therapy such as dose reduction/discontinuation of ongoing rescue medication or existing background therapy should be imitated. Reduction or discontinuation of ongoing rescue medication should be considered before a reduction in the dose of existing background therapy.

